9.5.3 Concomitant medication

Concomitant medication will be coded using the WHO drug dictionary (Version March 2017). Concomitant medication will be listed.

9.5.4 Clinical laboratory parameters

All clinical chemistry, hematology and urinalysis data will be listed. Additionally clinical chemistry, hematology and urinalysis data outside the reference ranges will be listed.

Values for any clinical chemistry, hematology and urinalysis values outside the reference ranges will be flagged on the individual patient data listings.

9.5.5 Vital signs

Vital signs data will be summarized by treatment together with changes from baseline, where baseline is defined as Day 1 predose of each period. Furthermore, values for individual patients will be listed.

9.5.6 Electrocardiogram (ECG)

The ECG data will be obtained directly from the 12-lead ECG traces. Where ECGs are measured in triplicate, the mean value will be used in all subsequent calculations. These data include the

PR, QT, QRS duration and heart rate. In addition, QTcF (the QT interval corrected using Fridericia's formula) will be calculated as follows:

$$QTcF = \frac{QT}{\sqrt[3]{(60/HR)}}$$

The ECG data will be summarized by treatment together with changes from baseline, where baseline is defined as Day 1 predose of each period.

A serum insulin lispro concentration-QT analysis will be performed to assess the changes from baseline (Day 1 predose of each period) QTcF interval relative to serum insulin lispro concentrations following administration of LY900014 and Humalog. BLQ concentration data will be removed prior to analysis. The analysis will be performed by plotting change from baseline QTcF against serum insulin lispro concentrations, including all post dosing timepoints. The plot will be produced separately for each treatment.

A mixed effects analysis model will be performed on the change from baseline QTcF values and will include serum insulin lispro concentrations as a covariate and subject as a random effect. The results of the model and associated 90% CI will be fitted on the plot and the p-value for the slope reported.

9.5.7 Hepatic Monitoring

If a patient experiences elevated alanine aminotransferase (ALT) $\geq 3 \times$ upper limit of normal (ULN), alkaline phosphatase (ALP) $\geq 2 \times$ ULN, or elevated total bilirubin (TBL) $\geq 2 \times$ ULN, liver tests will be performed to confirm the abnormality.

The patients' liver disease history and associated person liver disease history data will be listed. Any concomitant medication of acetaminophen/paracetamol will be listed. Results from any hepatic monitoring procedures, such as a magnetic resonance elastography (MRE) scan, and a biopsy assessment will be listed, if performed.

Hepatic risk factor assessment data will be listed. Liver related signs and symptoms data will be summarized by treatment and listed. Alcohol and recreational drug use data will also be listed.

All hepatic chemistry, hematology, coagulation, and serology data will be listed. Values outside the reference ranges will be flagged on the individual patient data listings.

9.5.8 Injection Site Local Tolerability Assessment

Injection site assessment data will be listed for individual patients and will be summarized in frequency tables by treatment and timepoint.

9.5.9 Visual Analog Scale (VAS) Assessment of Pain

The primary study assessment will be the intensity of pain at each injection site immediately after the injection (time 0) as reported by the patient and measured according to the 0- to

100-mm VAS. A Wilcoxon signed rank test will be used to analyze the time 0 (immediately after dosing) data. The difference in medians between LY900014 and Humalog and the 90% CIs for the difference will be presented. A descriptive summary will be provided for the following categories of scores: 0, 1-10, 11-20, 21-30, 31-40, etc. up to the maximum category by treatment for each time point.

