10.3.1.2.1. Statistical Evaluation of the Intensity of Injection-site Pain

The primary study assessment will be the intensity of pain at each injection site immediately after the injection (time 0) as reported by the patient and measured according to the 0- to 100-mm VAS. A Wilcoxon signed rank test will be used to analyze the time 0 (immediately after dosing) data. A descriptive summary will be provided for the following categories of scores: 0, 1-10, 11-20, 21-30, 31-40, etc. up to the maximum category by treatment for each time point.

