7. SAMPLE SIZE JUSTIFICATION

Up to 40 patients will be randomized in order that approximately 28 patients complete the study. Twenty-eight completing patients will provide approximately 92% power to demonstrate a 40% increase in the insulin lispro area under the concentration versus time curve (AUC) from time zero to 30 minutes (AUC[0-30min]) between LY900014 and Humalog. Testing will be done at an alpha level of 0.05 with a 2-sided confidence interval (CI). The variability was estimated by analyzing a Lilly internal study that showed a log-scale standard deviation (SD) of within-patient difference in AUC(0-30min) of 0.5. Analysis of internal data showed a log-scale SD of within-patient difference in time to early half-maximal serum concentration (early 50% t_{max}) of 0.5, which provides approximately 95% power to show a 30% reduction in early 50% t_{max} , testing with an alpha level of 0.05 and a 2-sided CI.

In addition, the study is adequately powered to evaluate the GD parameters. There is approximately 71% power to detect a 20% decrease in both time to onset of insulin action (T_{onset}) and time to early half-maximal GIR before time to maximum glucose infusion rate (TR_{max}) (early 50% TR_{max}), and approximately 81% power to detect at least a 40% increase in total amount of glucose infused over 30 minutes ($G_{tot}[0-30min]$) and total amount of glucose infused over 1 hour ($G_{tot}[0-1h]$). In estimations, the log-scale SD of within-patient difference was used with 0.45 for T_{onset} and early 50% TR_{max} , and 0.6 for $G_{tot}(0-30min)$ and $G_{tot}(0-1h)$.

Patients who discontinue from the study prior to completion of both treatment periods with evaluable primary outcome data can be replaced to ensure that enough patients may complete the study. The replacement patient will adopt the original patient's randomized treatment sequence.

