9.3.2 Pharmacokinetic Statistical Inference

Log-transformed C_{max} and AUC estimates for insulin lispro will be evaluated to estimate least squares (LS) geometric means, ratios of geometric means between LY900014 and Humalog, and their corresponding 95% CIs using the mixed-effects model that includes treatment, sequence, and period as fixed effects and patient within sequence as a random effect.

Example SAS code:

```
proc mixed data=pk;
class patient period treatment sequence ;
model logpk = treatment period sequence / ddfm=kr;
random patient(sequence);
lsmeans treatment;
run;
```

The same model without log transformation will be used for the analysis of the PK time parameters (early 50% t_{max} , late 50% t_{max} , and t_{max}). LS means, treatment differences in LS means, and the corresponding 95% CIs for the treatment differences will be estimated from the model. The treatment ratios and 95% CIs for the ratios will be calculated using Fieller's theorem.

Statistical significance will be achieved when the p-value for a test is less than 0.05.

The analyses described above will also be performed on the population of patients who completed and had evaluable PK data for both study periods.

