9.5.12 Safety and Tolerability Statistical Methodology

No inferential statistical analyses are planned.

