11. CHANGES FROM THE PROTOCOL SPECIFIED STATISTICAL ANALYSES

There were no changes from the protocol specified statistical analyses.

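### The pain VAS is tested with a paired signed-rank test but reported as a difference in medians with a 90% CI, so interval and p-value can disagree

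*SAP*

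**What the plan says.** Protocol 10.3.1.2.1 makes pain immediately after the injection, on the 0 to 100 mm VAS, the main pain assessment and names the test: "A Wilcoxon signed rank test will be used to analyze the time 0 (immediately after dosing) data". It plans no effect estimate and no interval. SAP 9.5.9 repeats the test and adds one sentence: "The difference in medians between LY900014 and Humalog and the 90% CIs for the difference will be presented". It does not say which difference in medians is meant, how the interval is built, or at what level the test is read.

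Four other places bear on this:

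- **SAP 9.3.2 (PK inference):** "Statistical significance will be achieved when the p-value for a test is less than 0.05". Protocol 10.3.2.2 has the same rule. SAP Section 7 uses a two-sided alpha of 0.05 for the sample size. No other significance level appears.
- **SAP 9.3.2 and 9.4.2:** the PK and GD treatment comparisons carry 95% CIs.
- **SAP 9.5.12 (safety methodology):** "No inferential statistical analyses are planned".
- **SAP Section 11:** "There were no changes from the protocol specified statistical analyses".

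**The concern.** There are two mismatches.

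The first is in the quantity. A signed-rank test on crossover data concerns the centre of the within-patient differences. A difference between the LY900014 median and the Humalog median is computed from two marginal distributions. It discards the pairing, and it can differ from the paired estimate in size and even in sign.

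The second is in the level. A 90% interval corresponds to a two-sided 10% test. Beside a p-value read at 0.05, it can exclude zero when the test is not significant.

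The stake is the reading of a tolerability result. Safety and tolerability of the commercial formulation is a secondary objective, and time-0 pain is the only safety measure with a formal between-treatment test. The report could show an interval and a p-value pointing different ways, with no rule for choosing between them. The programmer would also have to guess both the estimator and the interval method.

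**Working it through.** **1. Does 0.05 with 28 patients describe the plan?** The documents give no power for VAS pain, so this step checks only the working alpha and sample size. Inputs from SAP Section 7: 28 completers, ratio 1.40 for AUC(0-30min), log-scale SD of the within-patient difference 0.5, two-sided alpha 0.05.

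Noncentrality = ln(1.4) / (0.5/√28) = 0.3365 / 0.0945 = 3.56. The noncentral t distribution with 26 or 27 degrees of freedom gives 92.9% power, against a stated 92%. The figure reproduces.

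**2. Level mismatch, if the CI inverts the signed-rank test.** With n = 28 and no ties or zeros, the rank sums total 28 × 29 / 2 = 406. Let W be the smaller of the two signed rank sums. From the exact null distribution:

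- the two-sided 5% test rejects at W ≤ 116, exact level 0.0477;
- the 90% interval excludes zero at W ≤ 130, exact level 0.0993.

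With no true difference, the interval excludes zero while p exceeds 0.05 with probability 0.0993 − 0.0477 = 0.052. With normal within-patient differences (assumed) and true shifts of 0.2, 0.3, 0.4 and 0.5 SD, the simulated rates are 10.1%, 13.2%, 13.6% and 11.3%.

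One simulated data set shows the effect: p = 0.066, Hodges-Lehmann estimate 4.4 mm, 90% CI 0.45 to 9.1 mm, 95% CI −0.2 to 9.8 mm.

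**3. Quantity mismatch, if the CI is for the difference of treatment medians.** The documents give no VAS distribution, so this step rests on assumptions: skewed (log-normal) scores correlated within patient, 30% of scores set to zero, rounding to whole mm, a cap at 100, n = 28, zero differences dropped in the test, a percentile-bootstrap CI, and 1,000 trials per effect.

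| Log-scale effect | p < 0.05, zero inside 90% CI | p ≥ 0.05, 90% CI excludes zero | p < 0.05, zero inside 95% CI |
|---|---|---|---|
| 0 | 3.7% | 1.0% | 4.1% |
| 0.3 | 5.4% | 2.8% | 7.0% |
| 0.6 | 17.2% | 3.0% | 21.7% |

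The difference of treatment medians and the Hodges-Lehmann estimate had opposite signs in about 4% to 5% of trials. A repeat with 3,000 trials per effect gave 3.5%, 7.3% and 16.7% for the first column and 1.3%, 2.2% and 2.3% for the second.

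The last column shows that moving from 90% to 95% while keeping the same estimator does not remove the disagreement.

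**4. Does the proposed estimate agree with the test?** Without ties or zeros, a 95% Hodges-Lehmann interval uses the same cut-off as the 5% test (W ≤ 116), so they cannot disagree. With the zeros and ties of step 3, a 95% interval built from the no-ties cut-off disagreed with a test that drops zeros in 3.6%, 6.4% and 11.9% of the repeat trials. The rule for zeros and ties must therefore be common to both.

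**The case against.** The strongest reply is that no 5% decision exists for pain. The 0.05 rule stands under PK inference and in the sample size, and SAP 9.5.12 says safety has no inferential analysis. If the comparison is descriptive, there is nothing for the interval to contradict. This stands in part: 0.05 is carried over as the only level given. But SAP 9.5.9 does plan a test, so the two sections conflict, and the quantity mismatch remains without any level.

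The second reply is that the phrase may be loose wording for a paired estimate, perhaps settled in the table shells, which are not available here. That is possible. Only the level mismatch would then remain, and the text would still need to name the estimator.

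The third is that SAP Section 3 asks only for substantial differences from the protocol to be identified. An added summary of a planned test may not qualify, but the flat statement in Section 11 is still imprecise.

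A reader might also infer several stronger things that the documents do not support:

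- **That the 90% CI understates uncertainty.** An interval labelled 90% does not. It is narrower than a 95% interval (1.645/1.96 = 0.84 in the normal case), but openly so.
- **That 90% is out of line with the whole plan.** The SAP's other safety interval, for the concentration-QTcF model in 9.5.6, is also 90%. That one accompanies a slope, not a treatment comparison.
- **That the interval excludes zero in about 10% of null trials on any reading.** This holds only if it inverts the signed-rank test. For the difference of treatment medians, the repeat simulation gave 2.9%.

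**Conclusion.** The point holds as a moderate one about how a tolerability result is reported. As written, SAP 9.5.9 pairs a test of within-patient differences with an estimate that, read literally, ignores the pairing, at a confidence level that does not match the plan's only significance level. If the CI inverts the test, the two disagree in about 5% of trials with no true difference; this is exact for n = 28 without ties. If it is a CI for the difference of treatment medians, disagreement runs both ways, and the commoner form is p below 0.05 with zero inside the CI, at about 4% to 17%. Those last figures depend on the assumed VAS distribution and the bootstrap interval.

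Because the pain section calls time-0 pain its primary assessment, a reader might infer that a main trial conclusion is at risk. It is not. Protocol Section 4 lists AEs as the safety endpoint, pain plays no part in the sample size, and the PK and GD conclusions are unaffected.

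**What to change.** In SAP 9.5.9, replace the difference in medians and its 90% CI with the Hodges-Lehmann estimate of the within-patient difference (LY900014 minus Humalog) and a 95% CI obtained by inverting the same signed-rank test. State the two-sided 5% level there, and one rule for zero differences and ties that applies to both the p-value and the interval.

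Reword SAP 9.5.12 so that it excepts this test, and list the added estimate and CI in SAP Section 11.

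The cost is a few sentences and a somewhat wider interval. In the example above, the width goes from 8.65 to 10.0 mm. No new data or patients are needed.

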9.5.10 Immunogenicity

The frequency of antibody formation to insulin lispro will be determined. The relationship between the presence (or absence) of antibodies and AEs will be assessed.

9.5.11 Other assessments

All other safety assessments not detailed in this section will be listed but not summarized or statistically analyzed.

9.5.12 Safety and Tolerability Statistical Methodology

No inferential statistical analyses are planned.

10. INTERIM ANALYSES

No interim statistical analyses are planned.

11. CHANGES FROM THE PROTOCOL SPECIFIED STATISTICAL ANALYSES

There were no changes from the protocol specified statistical analyses.

13. DATA PRESENTATION

13.1 Derived Parameters

Individual derived parameters (e.g. PK parameters) and appropriate summary statistics will be reported to three significant figures. Observed concentration data, e.g. C_{max} , should be reported as received. Observed time data, e.g. t_{max} , should be reported as received. N and percentage values should be reported as whole numbers. Median values should be treated as an observed parameter and reported to the same number of decimal places as minimum and maximum values.

13.2 Missing Data

Missing data will not be displayed in listings.

13.3 Insufficient Data for Presentation

Some of the TFLs may not have sufficient numbers of patients or data for presentation. If this occurs, the blank TFL shell will be presented with a message printed in the centre of the table, such as, “No serious adverse events occurred for this study.”
